	The PI and study staff will provide any technical assistance regarding journaling for the participants and a direct number and email address for any additional issues that may potentially arise.
Intervener Training	Because all training content explained at baseline is uniform, and the journaling will be recorded in the journals at least twice a week, there will be no deviance in the provision of the program across participants.
Treatment Delivery & Receipt	A study-specific protocol will be developed and explicitly followed. Dosing (times per week the participant completed journals and practice) will be meticulously tracked by evaluating: the number of journal entries at least twice a week and the number of words written per journal entry in the hardcover journal. The journal will be given at week 0, and the journal will be collected after week 8 during the final appointment.
	We will limit the entries to six memories, with a target goal of 10-15 minutes spent journaling, and no set schedule (having entries occur in the morning or evening). The study staff will provide a weekly email reminder to enter a journal entry at least twice a week.
Treatment Enactment	We will follow participants from week 0 to week 8 to determine sustained use of the intervention (intermediate output).

Gratitude Intervention: The proposed study builds on Emmons and McCullough's original gratitude journaling intervention.⁴⁹ The original intervention, mostly undergraduate psychology students, did not include a goal-setting exercise and conducted daily gratitude journaling. However, prior cardiovascular health studies have found that interventions pairing optimism and gratitude with education and systematic goal-setting related to physical activity led to more physical activity, fewer hospital readmissions, and improved levels of inflammatory

Protocol Page 4 of 12

biomarkers.³⁶ Therefore, this study will pair the use of goal setting and physical activity education and to reduce the burden of journaling for cancer survivors and the participants will journal at least twice a week. During the initial session, the Principal Investigator or research assistant will provide a journal kit and an educational physical activity brochure to assist in setting 1-2 physical activity goals during the study period.

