Data Collection and Study Procedures: After screening for eligibility and collection of verbal consent, we will schedule an in-person appointment to collect baseline data, including collection of a blood sample (see Table 1 for measures and variables to be collected). Before the appointment, we will send demographic and cancer history questionnaires and self-report instruments (listed below) to participants for review. Informed written consent will be obtained at the in-person appointment, and an electronic survey will be sent following completion of the first appointment. After baseline (T1) data collection, participants will be randomized to either the gratitude journaling intervention or attention control group in a 1:1 ratio using online randomization software (http://randomization.com), and block randomization to ensure equal distribution between groups. The PI will inform participants of their group assignment and provide intervention details. The research assistant and biostatistician will be blind to group allocation. Participants will begin their daily intervention within 1 week of completing T1 data collection. They will also be scheduled for their T2 data collection appointment, which will occur 8 weeks after the start of the intervention and will include the same measures as baseline excluding the demographic and cancer history questionnaires. Data will be stored in Qualtrics on a secure university server and password protected with the assistance of the Biostatistics Core.

Blood Collection, Processing, and Storage: Blood samples will be obtained by a registered nurse or phlebotomist using the CTSI's standard protocol at the UF Clinical Research Center. After a ten-minute rest period, up to 10 ml of blood will be drawn. No more than two attempts will made to obtain blood samples with any participant. Blood samples will be collected, processed and stored with the OAIC Metabolism and Translational Science Core in the UF Clinical Research Center.

Table 1. Study Measures.

Outcome (Time Points)	Measure/Description
Demographics (T1)	Age, sex, education, marital status, body mass index; cancer- and treatment-related variables
	including time since diagnosis, cancer stage, grade and other disease-related variables including
	hormonal and HER2 status, surgical type, chemotherapy, radiotherapy, and cancer treatment.
Dispositional gratitude	The Gratitude Questionnaire-6 (GQ-6), a well-validated, self-administered 6-item scale, is

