The PI and research assistant will obtain informed consent, conduct participant screening, collect questionnaire data, monitor the experiment, implement the intervention, and ensure the safety of the participants. All procedures will be conducted by trained personnel. All persons responsible for the intervention will undergo thorough training. The laboratory is equipped with a telephone in case of an emergency, and in-house registered nurses (clinical research nurses) are also available. Emergency phone contacts will be posted in the laboratory's manual of operations, and all experimenters will be informed about who to contact in the event of emergencies. Participants will also be informed that multiple measures will be taken to ensure their safety. Participants may withdraw from the study at any time.

Description of Informed Consent. IRB approval will be obtained before participant recruitment begins. Potential participants will be administered a brief phone screening to assess their appropriateness for the study. During the call, they will receive a brief description of the study procedures, including information about the nature of the questionnaires and blood-draw collection and associated risks. If they agree to participate, the PI will review the details of the study with them and review the written informed consent in detail in a private research study exam room during the initial visit at T1. Women will participate in the study only after they provide verbal and written informed consent. The informed consent form will include standard information, including a description of the research protocol, the potential risks and benefits of participation, participant assurances, and contact information for the PI. Participants will also be informed that they can withdraw from the study at any time and that this will have no adverse impact on the study or their future medical treatment. Potential participants will be provided a copy of the informed consent form to review before being asked to sign. Informed consent will be documented via the participant's and investigator's signatures. A signed copy of the informed consent will be provided to participants during the initial visit.

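### The PI both enrols women and announces their assignment under block randomization, with no list holder or concealment step described, so foreknowledge of upcoming assignments cannot be ruled out

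*Combined protocol and SAP*

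**What the plan says.** Under Data Collection and Study Procedures, the sequence is: "After baseline (T1) data collection, participants will be randomized" to one of the two arms, "in a 1:1 ratio using online randomization software (http://randomization.com), and block randomization to ensure equal distribution between groups". The same paragraph continues: "The PI will inform participants of their group assignment and provide intervention details". It then adds: "The research assistant and biostatistician will be blind to group allocation".

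Under Adequacy of Protections Against Risks, the enrolment roles are: "The PI and research assistant will obtain informed consent, conduct participant screening, collect questionnaire data, monitor the experiment, implement the intervention". Under Description of Informed Consent, once a woman agrees by telephone, "the PI will review the details of the study with them and review the written informed consent in detail" at the T1 visit.

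Under Gratitude Intervention, at the initial session "the Principal Investigator or research assistant will provide a journal kit". The fidelity table under Study Design describes a different custom journal for each arm.

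The protocol does not state the block size, whether it varies, who generates the list, who holds it, or how each assignment is kept hidden until it is released.

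**The concern.** Randomization protects the comparison only if whoever decides on the next woman cannot tell which arm she would enter. Here one person, the PI, does the screening and consent and also learns every past assignment by announcing it. Blocked allocation carries information forward, because once one arm's places in a block are used up, the rest of that block is determined. The plan describes no barrier between that knowledge and the next enrolment decision.

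There is room for discretion before randomization. Both exclusion criteria (regular meditation or gratitude practice, and current activity level) depend on what is elicited at screening, and appointments can be scheduled earlier or later. With 14 women per arm, a few such choices could matter. Aim 1 sets 80% retention in each group: 11 of 14 is 78.6% and misses the target, while 12 of 14 is 85.7% and meets it. The Aim 2 effect sizes are meant to inform a larger trial, so any distortion would carry forward.

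**Working it through.** **Roles set side by side**

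| Task | PI | Research assistant | Biostatistician |
|---|---|---|---|
| Screens and obtains consent | yes | yes | not stated |
| Reviews written consent at T1 | yes | not stated | not stated |
| Announces the assignment | yes | not stated | not stated |
| Declared blind | no | yes | yes |
| Generates or holds the list | not stated | ruled out if blind | ruled out if blind |

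Of the three roles that the allocation paragraph mentions, only the PI is left to run the website and keep the list. The Biostatistics Core is named as a resource but is given no part in allocation.

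**Length of the list.** The planned total is 28. The title of the cited rule-of-thumb paper gives 12 per group. With 10% attrition, 12/0.9 = 13.3, rounded up to 14 per arm, and 2 × 14 = 28, as the plan states. It is used here only as the length of the list. The 26 under Inclusion of Women does not affect the argument.

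**Predictability.** Block size is an assumption, so a range is shown. Take a fixed block of size 2m, known to someone who sees all past assignments.

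- Expected share known with certainty: 1/(m + 1).
- Expected share guessed correctly by always naming the arm with more places left in the block: [m + 2^(2m−1)/C(2m, m) − 1/2]/(2m).

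For blocks of 4 (m = 2), the certain share is 1/3 and the correct share is (2 + 8/6 − 0.5)/4 = 2.833/4 = 70.8%.

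| Block size | Certain | Certain, of 28 | Guessed correctly |
|---|---|---|---|
| 2 | 50% | 14.0 | 75% |
| 4 | 33% | 9.3 | 71% |
| 6 | 25% | 6.1 | 68% |
| 8 | 20% | 4.8 | 67% |
| 14 | 12.5% | 3.5 | 63% |
| 28 | 6.7% | 1.9 | 60% |

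The percentages refer to complete blocks. The counts allow for an incomplete last block, since 28 is not a multiple of 6 or 8. For blocks of 6, four full blocks give 4 × 1.5 = 6.0. The fourth place of the fifth block is certain only if its first three are alike, with probability 2/20 = 0.1, so the total is 6.1. For blocks of 8, three full blocks give 3 × 1.6 = 4.8, and the four remaining places add nothing.

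**Does varying the block size cure it?** Lists of 28 were simulated (40,000 per setting) with block sizes drawn at random and unknown to the guesser. The guesser names the arm with fewer women so far and tosses a coin when the arms are level. Correct guesses were 72.0% for sizes 2 and 4, 68.7% for 4 and 6, and 69.8% for 2, 4 and 6. Withholding varied sizes makes it harder to be certain, but the running imbalance still gives roughly 70% correct.

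**Order of events at T1.** Data Collection and Study Procedures sends the electronic survey after the first appointment. The Attrition paragraph has the questionnaires gathered during the T1 visit. Gratitude Intervention provides the journal kit in the initial session. Read together, these leave it possible that a woman holds her arm's journal before she completes the baseline survey.

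**The case against.** The strongest reply is that the decisive facts are absent, not adverse. A Core member may run the website, block sizes may vary, and the PI may never see the list. That stands: the documents show missing concealment, not foreknowledge. It does not remove the point, because the roles they do assign put enrolment and disclosure in one unblinded person.

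Second, randomization follows written consent and T1 collection. This is a real protection, but it does not stop someone who can predict the next assignment from acting at telephone screening, scheduling or consent, and the timing of the baseline survey is itself unclear. Any effect on baseline measurement should not be pressed: the instruments are self-report, blood is drawn by a nurse or phlebotomist, and the assays are done in a laboratory.

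Third, the planned treatment-by-time models partly account for measured baseline differences. They do so only for what is measured, and not for motivation or willingness to commit.

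Fourth, this is a pilot that admits it may be underpowered. That limits the consequences, but the per-group retention target and the effect sizes still rest on the randomized comparison.

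A reader might infer more than the text supports:

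- **That everyone who enrols also conveys assignments.** Only the PI is said to do so, and the research assistant is declared blind.
- **That the trial is open.** The documents never call it that. Participants are told their group, but partial blinding is stated.
- **That recruitment figures would shift.** The feasibility proportions under Data Analysis are not defined by arm, and no route from guessing the arm to those figures is shown.

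**Conclusion.** The point holds as a gap in allocation concealment that the plan's own roles make consequential. The PI screens, consents and announces each assignment under block randomization, no other unblinded person is given a part in allocation, and no concealment step is described. It would go too far to say that assignments will be foreseen or that enrolment will be biased. The documents support only that neither can be excluded.

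The size depends on a block size the documents do not give. If it is fixed and known to the PI, between 50% (blocks of 2) and 7% (one block of 28) of assignments would be certain, and between 75% and 60% would be guessed correctly. If sizes are mixed and unknown, about 69% to 72% could still be guessed by someone who sees every past assignment.

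A related inconsistency needs settling. The research assistant is declared blind, yet may hand over the kit, which breaks the blinding if the kit holds the arm-specific journal, and is listed among those who implement the intervention.

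**What to change.** Amend Data Collection and Study Procedures to state that:

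1. A Biostatistics Core member other than the blinded biostatistician generates and holds the list. Block sizes are varied and withheld from the PI and research assistant, and are not printed in any document they use.
2. The list is loaded in REDCap, which the Data- and Safety-Monitoring Plan already names. Each assignment is released only after written consent and all T1 data, including the electronic survey, are complete and locked.
3. Where existing staffing allows, someone who does not screen or consent discloses the assignment. This step deals with guessing from the running imbalance, which varying block sizes does not.
4. The research assistant's blinding is reconciled with handing over the kit and implementing the intervention, either by reassigning those tasks or by withdrawing the claim of blinding.

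The release rule means that the survey is either completed at the T1 visit, as the Attrition paragraph implies, or the journal is supplied afterwards. The plan's one-week window between T1 completion and the start of journaling leaves room for the second option. The three passages on T1 timing should be made to agree.

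The cost is a few sentences, modest set-up time, and some time from a second Core member. Arm sizes may differ by a few women if the last block is incomplete.

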Aim 1. Assess the feasibility and acceptability of a gratitude journaling intervention using a pilot randomized controlled trial (RCT) two-group parallel design over eight weeks. We hypothesize that among the 28 participants 1) at least 80% of the participants in both arms will report the study to be acceptable, 2) biomarker collection will be completed in at least 80% of the surveys and the retention rate will be 80% in each group, and 3) physical activity, health markers, gratitude, well-being, and distress will improve over time in the gratitude intervention group than those in the attention control group.

Aim 2. Describe differences and distributions of outcome variables and effect size for the gratitude journaling intervention compared to the attention control group on dispositional gratitude, spiritual well-being, psychological distress, exercise readiness, mental and health behaviors in AA women (Superwoman Schema), and inflammatory biomarkers from baseline to post-intervention.

Research Plan:

We will conduct a pilot feasibility study for the gratitude intervention using a two-group parallel randomassignment experimental design to achieve our aims. We will use resources from the Clinical Research, Metabolism and Translational Science, and Biostatistics Cores of the UF Older Americans Independence Center's (OAIC) / UF Clinical and Translational Science Institute (CTSI) to conduct this study.

Study Participants: As per the recommendation of Julious⁴⁸ for 14 participants per group for a pilot study due to no prior information to base a sample size, we will recruit 28 participants for this two-group study to account for a potential attrition rate of 10%. We will recruit AA women from all socioeconomic groups with a history of BC Protocol

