(T1, T2)	designed to measure four facets of dispositional gratitude: ⁴⁹ (a) intensity, (b) frequency, (c) span
	and (d) density. Each item is rated on a 7-point Likert-type scale ranging from 1 (strongly
	disagree) to 7 (strongly agree).
Spiritual Well-Being	The Functional Assessment of Chronic Illness Therapy - Spiritual Well-Being 12 Item Scale
(T1, T2)	(FACITsp12) is a 12-item scale designed to assess spiritual well-being over the past 7 days in a
	population with a chronic illness. ⁵⁰ Items are rated on a Likert-type scale ranging from 0 (not at all)
	to 4 (very much).
Distress	The Perceived Stress Scale (PSS), used to measure stress, consists of 10 items rated on a 5-
(T1, T2)	point Likert scale ranging from 0 (never) to 4 (very often) during the last month.

Outcome (Time Points)	Measure/Description
Superwoman schema	The Giscombe Superwoman Schema Questionnaire (G-SWS-Q) was developed to measure
(racial and gender	components prominent in the superwoman schema construct. ^{6,51} It contains 35 statements rated
identity)	from 0 (not true) to 4 (true all the time) across the 5 subscales of (1) obligation to present an image
(T1, T2)	of strength, (2) obligation to suppress emotions, (3) resistance to being vulnerable, (4) intense
	motivation to succeed and (5) obligation to help others. Higher scores indicate higher agreement
	with the identity.
Exercise readiness (self-	Exercise readiness will be assessed using the Stage of Motivational Readiness for Physical
efficacy and stages of	Activity questionnaire, a highly reliable instrument with 5 items that classify a person as being in
exercise behavior	the pre-contemplation, contemplation, preparation, action, or maintenance stage of exercise
change) (T1, T2)	behavior change. ⁵²
TNF-α, IL-6, GDF15 (T1,	Luminex panel
T2)	
CRP (T1, T2)	Enzyme-linked immunosorbent assay (ELISA) kit
Treatment satisfaction	The Client Satisfaction Questionnaire (CSQ) is a standard measure used across health care
(T2)	delivery and will be used to assess the acceptability of the gratitude intervention. ⁵³

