Separate two-by-two mixed-effects general linear models (GLMM),⁵⁴ comprised of effects for treatment, time, and treatment-by-time interaction, will be used to estimate effect sizes for each of the outcome variables. The distribution of residuals will be evaluated for the tenability of model assumptions, and, where necessary, remedial measures such as Box-Cox transformations will be applied. CONSORT guidelines for intent-to-treat principles will be used for hypothesis testing to manage missing data related to attrition. We will determine differences between groups using t-tests.

6. Possible Discomforts and Risks: Protection of Human Subjects

PI Version: 09/21/2022

According to federal regulations and NIH policy, applications that propose to involve human subjects must address risks to human subjects (human subject characteristics, involvement and design; sources of materials; and potential risk); adequacy of protection against risks (recruitment and informed consent and

Protocol IRB version 03.09.04 protections against risk); potential benefits of the proposed research (are potential risks to subjects reasonable in light of anticipated benefits?); the importance of the knowledge to be gained; and a data- and safety-monitoring plan/board. We address each of these requirements below.

Risks to Human Participants

Inclusion/Exclusion Criteria. Table 2 lists study inclusion/exclusion criteria. Exclusion criteria are designed to prevent inclusion of participants who would experience discomfort or harm during collection of blood or other data and to protect the data integrity of the participants.

Table 2. Inclusion and Exclusion Criteria.

Inclusion Criteria

- Self-report as AA or Black
- English speaking
- History of BC (Stage I–IV); 3 months to 6 years post-adjuvant chemotherapy
- Participants on hormonal therapies or HER-2 therapy are acceptable

Exclusion Criteria

- Self-reported regular meditation or gratitude practices (more than once a week for at least a month)
- Meeting the CDC's physical activity guidelines (at least 150 min of moderate-intensity aerobic physical activity or 75 min of vigorous-intensity physical activity, or an equivalent combination each week)

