Blood-draw collection. Although generally safe, blood-draw collection procedures can confer limited risks, including that a participant will experience pain or discomfort. To minimize discomfort, we will make no more than two attempts per time point to obtain blood samples with any one participant.

Onsite adverse events. In the event of any of the following adverse events, we will immediately notify a physician and the IRB: 1) deaths, 2) falls, or 3) health events that result in immediate hospitalization or medical care.

Attrition. Given the success of the studies conducted at the UF OAIC Clinical Research Core, we do not expect any recruitment issues. However, since this proposal requires two visits to the institute, we are anticipating 5%–10% attrition. We will thus gather all primary data (blood draw and electronic questionnaires) during the T1 visit. At the T2 visit, we will collect another blood draw and the electronic questionnaires and conduct exit interviews and administer the CSQ to evaluate usability, usefulness, and participant satisfaction. Both structured and openended questions will be used to assess participants' perception of the intervention's content, value, structure, and burden. To further minimize attrition, we will (1) educate participants during the initial telephone screening about the importance of committing to the study, (2) obtain complete contact information (including alternative email addresses and phone numbers), (3) place a reminder call and/or email (if available) 2 days before the scheduled visit, and (4) provide compensation upon completion of each visit.

Inadequate Sample Size. Since this is a pilot feasibility study, which requires a relatively small sample, it may be underpowered to detect statistically significant differences in outcome measures. However, it will provide the information necessary to design future adequately powered efficacy studies.

Adequacy of Protections Against Risks

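### Aim 1 places a directional efficacy hypothesis on five domains inside a feasibility aim, with tests but no error control, and 14 per arm cannot yield a dependable effect size for the next trial

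*Combined protocol and SAP*

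**What the plan says.** - **Specific Aims, Aim 1** is labelled feasibility and acceptability. Its first two hypotheses concern rates (acceptability, biomarker completion, retention). The third is a between-arm claim: "physical activity, health markers, gratitude, well-being, and distress will improve over time in the gratitude intervention group than those in the attention control group".
- **Specific Aims, Aim 2** is descriptive: "Describe differences and distributions of outcome variables and effect size for the gratitude journaling intervention compared to the attention control group". It covers a wider outcome list that includes exercise readiness and the Superwoman Schema.
- **Data Analysis** defines feasibility by three proportions: more than 75% of women approached meeting criteria, more than 80% completing baseline measures, and more than 80% of those completing the post-intervention assessment. No efficacy result is among them.
- **Data Analysis** then fits a separate mixed model (treatment, time, treatment-by-time) to each outcome to estimate effect sizes. It says intent-to-treat principles "will be used for hypothesis testing", and closes with t-tests for group differences, naming neither outcome nor time point. Alpha, sidedness, primary outcome, multiplicity rule, confidence intervals and a success rule for the third hypothesis are all absent.
- **Inadequate Sample Size** (section 6) concedes that "it may be underpowered to detect statistically significant differences in outcome measures", then says without qualification that "it will provide the information necessary to design future adequately powered efficacy studies".

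**The concern.** The third hypothesis of Aim 1 is the only one in the plan that compares the arms, so the hypothesis testing and t-tests in Data Analysis most naturally attach to it. Nothing says how many outcomes must be significant, at what level, or with what allowance for testing several. Conceding low power deals with missed effects. It does not guard against one chance result among several being reported as support for Aim 1.

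The second risk is to the next trial. In a sample this small a difference reaches significance only if it is large, so effect sizes picked out by significance will tend to be exaggerated. An unqualified promise of design information leaves room to use such an estimate in the next sample size calculation.

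**Working it through.** **The plan's own figure.** Study Participants gives 14 per group, 28 in total, allowing for 10% attrition. The title of the reference cited for this rule says 12 per group. 12 / (1 − 0.10) = 13.3, rounded up to 14 per group; 2 × 14 = 28. The figure reproduces with 12 as the base. If 14 were the base, 14 / 0.90 = 15.6, or 16 per group and 32 in total. The sample to judge is therefore 14 per arm at best and about 12 after attrition.

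**Outcome count.** The five domains of the third hypothesis map to Table 1 as gratitude (1), spiritual well-being (1), stress (1) and biomarkers (TNF-α, IL-6, GDF15, CRP: 4). Physical activity has no measure in Table 1; with exercise readiness standing in, the total is 8.

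**False positives.** Assumptions, since the plan gives none: two-sided 0.05 per test, one test per outcome, no true effects, and any one significant outcome read as success.
- Independent outcomes: 1 − 0.95^8 = 0.337.
- Independent, favouring gratitude only: 1 − 0.975^8 = 0.183.
- Correlated outcomes, by simulation of two-sample t-tests at 14 per arm with a common correlation:

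| Correlation | Any significant | Any favouring gratitude |
|---|---|---|
| 0.3 | 30% | 15% |
| 0.5 | 25% | 13% |
| 0.7 | 20% | 10% |

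Analysing each outcome by both model and t-test would raise these somewhat; the two analyses of one outcome are strongly related.

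**Precision of the effect.** At a single time point the 95% half-width in SD units is t(0.975, 2n − 2) × √(2/n).
- 14 per arm: 2.056 × √(2/14) = 0.78. Power for 0.5 SD is 25%.
- 12 per arm: 2.074 × √(2/12) = 0.85. Power for 0.5 SD is 22%.

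With complete data the treatment-by-time contrast is a difference in mean change. With equal SDs at T1 and T2 and within-person correlation r, the half-width is multiplied by √(2(1 − r)). The plan gives no r, so a range is shown for 14 per arm:

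| Assumed r | Half-width (SD) | Power for 0.5 SD |
|---|---|---|
| 0.3 | 0.92 | 19% |
| 0.5 | 0.78 | 25% |
| 0.7 | 0.60 | 38% |
| 0.8 | 0.49 | 52% |

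At a single time point, an observed 0.5 SD with 14 per arm has a 95% CI of about −0.26 to 1.25 (noncentral t).

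**Consequence for the next trial (illustration).** In a single-time comparison at 14 per arm, p < 0.05 requires an observed difference of about 0.78 SD. If the truth were 0.5 SD and the next trial were sized on 0.78, 28 per arm would appear to give 82% power. The real power would be 45%; 80% needs 64 per arm.

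**What the pilot can supply.** The 95% CI for the pooled SD on 26 df is the estimate times √(26/41.92) = 0.79 to √(26/13.84) = 1.37. Sample size scales with the variance, so the upper limit implies 1.37² = 1.88 times as many participants. Retention of 23/28 (82%) has a 95% CI of 63% to 94%. Both are wide but usable for planning.

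**The case against.** The strongest reply is that this is an openly modest pilot. The mixed models are there to estimate effect sizes. The hypothesis-testing phrase sits in a sentence about missing data and sets no decision rule. The t-test sentence names no outcome. The feasibility criteria contain no efficacy result, and low power is admitted.

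Much of that is fair, and it rules out several stronger readings that a reader might infer:
- *That Aim 1 tests nine or more outcomes.* Nine is the Table 1 total at T1 and T2. The ninth, the Superwoman Schema, belongs only to the descriptive Aim 2, and nothing says its five subscales will be tested separately.
- *That a false positive is likely.* The figures are 20% to 34%, and 10% to 18% in favour of gratitude. They also need an assumed alpha and an any-one-counts rule. If every domain had to be significant, false positives would be very rare and power would be the difficulty instead.
- *That the feasibility verdict depends on efficacy tests.* The stated criteria do not include them.
- *That the pilot gives the next trial nothing, or that its effect size is already earmarked for the sample size.* Rates and SDs are obtainable, and no passage says how the effect size will be used.

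What the reply leaves standing is that Aim 1 lists an efficacy hypothesis beside the acceptability and retention hypotheses, that tests are planned without a rule for reading them, and that the promise to future trials does not separate what can be estimated usefully from what cannot.

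**Conclusion.** The point holds as a cheap improvement to the wording. A between-arm efficacy hypothesis is misplaced in a feasibility aim, and its tests carry no error control. The chance of at least one false positive over about eight outcomes is several times the nominal 5%, though well short of even odds. That size rests on the assumed 0.05 level, the assumed success rule, and exercise readiness standing in for physical activity.

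The precision conclusion is firmer. Across T1–T2 correlations of 0.3 to 0.8, power for 0.5 SD ranges only from about 19% to 52% even with all 14 per arm retained. The statement about informing future trials is therefore sound for feasibility rates and SDs, with wide intervals, and unsound for effect size.

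**What to change.** - **Aims:** move the third hypothesis from Aim 1 to Aim 2 and label it exploratory. Say which Table 1 measure represents physical activity.
- **Data Analysis:** report one between-arm estimate per outcome, the mixed-model treatment-by-time contrast, with its 95% CI, and the SD with its CI. Let this replace the separate t-tests and the hypothesis-testing wording. State that no efficacy conclusion will be drawn.
- **Inadequate Sample Size:** say that the pilot will supply recruitment, retention, adherence and SD estimates with stated precision, and that the observed effect size will not by itself size the next trial.

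This needs no new data, visits or participants. The sponsor gives up efficacy p-values that the design cannot support. Keeping a fully specified t-test is possible, but it would add little to the model contrast and would still need an error-control rule.
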